- 40 (2) Genome-wide association and DNA sequencing studies will identify genetic determinants
41 for COPD susceptibility that will provide insight into clinically relevant COPD subtypes.
- 42 (3) Distinct genetic determinants influence the development of emphysema and airway
43 disease.

44 **COPDGene Phase 3**

45 COPDGene has been funded for an additional five years by the US National Heart, Lung, and
46 Blood Institute as well as the COPD Foundation. In addition to the cross-sectional subject data
47 collected in the baseline and five year follow up COPDGene study visits, disease progression
48 and incidence of COPD in smokers are important additional endpoints for genetic association
49 studies. In Phase 1, we have completed enrollment of 10,371 subjects. In Phase 2, we have
50 completed 5,835 return visits and an additional 574 other follow up methods. For Phase 3, we
51 now propose to invite these subjects to return for a third evaluation ten years after their initial
52 visit to assess disease incidence and/or progression in COPDGene subjects.

53 **II. SPECIFIC AIMS**

54 The current specific aims for Phase 3 of COPDGene are included in this section.

55

56 **Specific Aim 1: Disease Progression**

57 All subjects who return for a 10-year visit and those who expire between the 5 and 10-year visits
58 will be analyzed to confirm prognostication of clinical disease progression. We estimate that
59 6,500 subjects will be analyzed in this aim; 4,500 subjects who return for a 10-year visit and
60 2,000 who expire before that visit.

61

62 **Specific Aim 2: Mortality and Incident Disease**

63 All 10,371 subjects enrolled in Phase 1 will be included to identify genetic, transcriptomic, and
64 proteomic determinants of susceptibility and progression of specific COPD subtypes. All these
65 subjects have had an initial visit but may or may not have visits at 5 and 10 years.
66 Through the longitudinal follow-up (LFU) program conducted twice a year since the initial visit,
67 we have obtained follow-up data from 82.3% of the original 10,371 subject cohort by a
68 combination of telephony, web survey or coordinator calls. We will continue LFU on all of the
69 original 10,371 subjects who are alive. All subjects will continue to be followed to assess vital
70 status. We will perform death searches at least yearly to identify subjects that have expired.
71 Death certificates, medical records and informant interviews will be obtained to determine cause

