72 of death.

73

74 **Specific Aim 3: Rapid Disease Progression Subtypes (Short Term Follow-up Study)**

75 To test high-risk subtypes for rapid COPD progression, approximately 800 subjects from the full
76 COPDGene cohort will participate. These subjects will be invited back for a Short Term Follow
77 up Study visit approximately one year after the Phase 3 visit.

78 Subjects participating in the Short-Term Follow-Up study will be identified by the Data
79 Coordinating Center and a list will be provided to each participating clinical center.

80 III. SUBJECT SELECTION- Phase 3

81 In summary, Phase 3 is the 10-year and 11-year (short-term follow up for applicable subjects)
82 return visit. Phase 3 is also the 5-year return visit for Non-Smokers enrolled in Phase 2.

83

84 All subjects to be studied have been enrolled in the Genetic Epidemiology of COPD Study
85 (COPDGene) in previous phases. As part of their original informed consent for COPDGene and
86 subsequent consent at the 5-year follow-up visit, subjects have provided consent to be re-
87 contacted for periodic follow-up and for other studies.

88 This project will invite all 10,371 subjects who are alive and still in the study who successfully
89 completed a Phase 1 visit for a Phase 3 study visit. At the time of writing this protocol, there are
90 1,573 deceased subjects. All non-smokers enrolled in Phase 2 will also be eligible to return for a
91 visit 5 years (\pm 6 month) after their first visit, in total 349 new non-smokers were enrolled in
92 Phase 2. This is a total of 10,720 subjects in the cohort. Phase 3 will be scheduled 10 years (\pm 6
93 months) after Phase 1 or 5 years (\pm 6 month) after Phase 2 (for new subjects enrolled in Phase 2).
94 There must be at least 3 years in between the Phase 2 and Phase 3 visits. Visits later than the
95 scheduled return visit *are* permitted. The Short-Term Follow-Up Study for rapid progressors
96 will occur approximately one year after the subject participates in the Phase 3 study.

97 A key component of the project is to establish contact with all of the previously enrolled subjects
98 who remain in the study or confirm the subjects are deceased. Clinical centers will utilize locally
99 stored contact information including secondary contacts to establish contact.

100 Eligible subjects will be contacted mail, email and/or phone and invited to participate in Phase 3

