242 The below table summarizes each phase of COPDGene.

Phase 1- COMPLETED	Phase 2- COMPLETED	Phase 3a- current project	Phase 3b- Short Term Follow Up -current project	Phase 3 Modified COVID-19

Visit 1 for all subjects
 
n=10,371 enrolled
	
Phase 1 subjects followed up in Phase 2
 
n=6,409
	
Will invite all subjects alive and still in the study from Phase 1 back for Phase 3
	
Select group of up to 800 subjects characterized as rapid progressors from analysis of the Phase 2 data will be invited for a Short –Term Follow-Up study to occur approximately 1 year after the subject is due/returns for their Phase 3 (Phase 3a) study visit.
	
Will invite all subjects alive, still in the study from Phase 1, and have not yet completed a Phase 3 visit for a virtual visit over the phone to answer some of the questionnaires. Later, those subjects will be brought on-site to complete in-person portion of the visit.
 
All subjects will be invited to provide updated information and medical records through a new questionnaire about respiratory illnesses

	New Non-smoking Subjects enrolled n=349	All 349 nonsmokers enrolled in Phase 2 will be invited back for Visit 2 (5 year follow up)		and COVID associated illnesses or abnormal test results.
		New Nonsmokers will be recruited		

243
244 All subjects previously enrolled in Phase 1 have provided consent with their initial study
245 enrollment to be contacted again for further research studies. Subjects will be sent an invitation
246 letter advising them that funding has been provided for the Phase 3 visit and informing them that
247 they will be contacted to schedule an appointment. Information learned from previous phases of
248 COPDGene will be included in this initial contact.

249 A telephone call will be made to each subject to schedule a date for his/her next study visit and
250 ask them to bring the following to the study visit:

- 251 1) all of their current oral and inhaled medications,
- 252 2) names of any injectable study medications received on a regular basis,
- 253 3) social security number,
- 254 4) name, address, and phone number of their personal physician,
- 255 5) name, address, and phone of two other individuals likely to know the subject's
256 whereabouts, at least one of whom is a relative not living with the subject, and
- 257 6) driver's license or other identification to assure they are the individual previously

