	20	40	60	80
Odds ratio of 2.25	24.3	43.1	68.2	82.7
Odds ratio of 2.5	32.1	58.8	84.9	95.4

773
 774
 775 We will also perform epidemiological and Omics analysis in 800 subjects from the Short-Term
 776 Follow-Up Study Population. The relationships between the outcomes of interest (FEV₁ and
 777 adjusted lung density) of each of the three high risk groups compared to the reference group will
 778 be assessed using linear mixed models. Covariates in these analyses will include risk group, visit,
 779 age, gender, pack-years of smoking, current smoking status, and baseline FEV₁ % predicted. The
 780 relationship between changes in FEV₁ and changes in adjusted lung density will be assessed by
 781 including time-varying as well as subject mean values in the model as predictors. An
 782 unstructured covariance structure (or other appropriate structure) will be used in the model to
 783 account for repeated measures. We will adjust for multiple statistical testing by requiring
 784 $p < 0.01$ to demonstrate any significant association.

785
 786 The power estimates to detect differences in change in FEV₁ or adjusted lung density for the
 787 Short-Term Follow-Up Study are shown in **Table 4**. Two rapid progression groups will be tested
 788 for change in FEV₁ (High COPD Progression Score and Paraseptal Emphysema) and two rapid
 789 progression groups will be tested for change in adjusted lung density (High Risk Airway Disease
 790 Axis and Paraseptal Emphysema). Based on the five-year changes in those groups compared to
 791 non-high risk subjects, 200 subjects per group will provide excellent power to detect differences
 792 between the rapid progression and non-high risk groups over one year. Power to detect
 793 differences for RNA-Seq and proteomic biomarkers between 200 rapid progression and 200 non-
 794 rapid progression subjects was assessed. We will have 80% power to detect effect sizes > 0.6
 795 standard deviations, which will be adequate to detect useful biomarkers.

796

Outcome	Rapid Progression Group	Sample Size of Each Short-Term Follow-Up Group		
		100	200	300
FEV ₁ , ml/yr	High COPD Progression Score	100	100	100
	Paraseptal Emphysema	72	95	99
Adjusted Lung Density, per yr	High Risk Airway Disease Axis	100	100	100
	Paraseptal Emphysema	100	100	100

797
798
799
800
801
802
803
804
805
806

VIII. RISKS AND DISCOMFORTS

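### The protocol uses 800 for the Phase 3b subjects invited, participating and analysed, so the 95% power for FEV1 in paraseptal emphysema leaves no room for non-return

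*Protocol*

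**What the plan says.** Three places in the protocol use the figure 800 for Phase 3b.

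- **Section IV, table of phases, Phase 3b column:** 800 is a ceiling on invitations. The entry opens with "Select group of up to 800 subjects characterized as", names them as fast progressors, and says that the people so identified "from analysis of the Phase 2 data will be invited for a Short –Term Follow-Up study".
- **Section II, Specific Aim 3:** 800 is the number taking part. The aim begins with "To test high-risk subtypes for rapid COPD progression, approximately 800 subjects from the full". Its next sentence says that these same people will be invited.
- **Section VII, Short-Term Follow-Up analysis:** 800 is the number analysed. The paragraph opens with "We will also perform epidemiological and Omics analysis in 800 subjects from the Short-Term".

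Section VII compares three high-risk groups with a reference group and states that "200 subjects per group will provide excellent power to detect differences". Table 4 supports this with power at 100, 200 and 300 per group. The FEV1 row for paraseptal emphysema reads 72, 95 and 99%. The other three rows read 100% throughout. The significance level behind Table 4 is not stated. The analysis paragraph just before it requires p<0.01 as its adjustment for multiple testing.

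**The concern.** Four groups of 200 make 800, so the column of Table 4 on which the power claim rests needs 800 analysed subjects. If 800 is also the most that will be invited, the claim assumes complete attendance. The protocol states no allowance for non-return and no replacement rule. It says only that the Data Coordinating Center will give each center a list.

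At stake is the one Table 4 comparison whose power depends visibly on group size. If fewer than 200 per group are analysed, the 95% is overstated for that comparison, and a non-significant result there would be less informative than the protocol suggests.

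**Working it through.** **Inputs**

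- Groups: 3 high-risk + 1 reference = 4 (Section VII). 4 × 200 = 800.
- Stated power, FEV1, paraseptal emphysema: 72 / 95 / 99% at 100 / 200 / 300 per group (Table 4).
- Significance criterion for this analysis: p<0.01 (Section VII).
- Effect size and SD behind Table 4: not given, so solved from the row itself.
- Return rate for Phase 3b: not given. Values below are assumptions.

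**Step 1. Reproduce the plan's row.** For two equal groups of n and a standardised difference d, the normal approximation is

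power = Φ(d·√(n/2) − z), with z = 1.960 at two-sided 0.05 and 2.576 at two-sided 0.01.

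Setting power to 72% at n = 100 and two-sided 0.05 gives d = 0.3596. Then:

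- n = 100: Φ(2.543 − 1.960) = 72.0%
- n = 200: Φ(3.596 − 1.960) = 94.9%
- n = 300: Φ(4.404 − 1.960) = 99.3%

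This matches 72 / 95 / 99. Values of d from about 0.358 to 0.362 fit all three cells after rounding. At two-sided 0.01, solving 72% at n = 100 gives 72 / 97.1 / 99.8%, and no d fits all three cells. The row is therefore consistent with 0.05 and not with the p<0.01 criterion.

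**Step 2. Choose return rates for a sensitivity range.** 90% and 95% represent modest one-year loss. Two lower values come from the protocol's figures for other visits. Section I reports that Phase 2 "completed 5,835 return visits and an additional 574 other follow up methods". Specific Aim 1 expects that "6,500 subjects will be analyzed in this aim; 4,500 subjects who return for a 10-year visit and" 2,000 who die before it.

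- 4,500 / 5,835 = 77%
- 4,500 / (10,371 − 2,000) = 4,500 / 8,371 = 54%

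**Step 3. Apply them to 200 invited per group, same d.**

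| Return | n per group | Power, two-sided 0.05 | Power, two-sided 0.01 |
|---|---|---|---|
| 100% | 200 | 95% | 85% |
| 95% | 190 | 94% | 82% |
| 90% | 180 | 93% | 80% |
| 77% | 154 | 88% | 72% |
| 54% | 108 | 75% | 53% |

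For example, at n = 154: 0.3596 × √77 = 3.156. Φ(3.156 − 1.960) = 88% and Φ(3.156 − 2.576) = 72%.

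**Step 4. Other claims on the 800.** The table of phases describes all 800 as rapid progressors, which leaves no place for the reference group that Section VII needs. The COVID-19 Adaptation text in Section VI adds subjects with reported respiratory exacerbations to Phase 3b, with no stated change to the total.

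**The case against.** The strongest reply is that 800 invitations is only one reading. Specific Aim 3 says that about 800 will take part and Section VII analyses 800, so the sponsor may mean 800 completers. That stands, and it is why the point is a conflict between three places and not a shown shortfall. The table of phases can also be read as 800 rapid progressors in three groups, with the reference group outside the total. That gives 800 / 3 = 267 invited per group, of whom 77% is about 206 and 54% about 143. On that reading the 800 analysed in Section VII, reference group included, no longer matches, so reconciliation is still needed.

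A reader might infer that the protocol's own figures show attendance of 54-77%, and hence far fewer than 200 per group. The documents do not support that. Both rates describe the whole cohort at 5- and 10-year visits, whereas Phase 3b follows Phase 3 by about one year. The 54% includes people who did not return after Phase 1, although Phase 3b subjects are selected from Phase 2 data. The 77% does not remove deaths from its denominator, so it is not an upper limit among survivors. One-year return could be 90% or higher.

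A reader might also extend the point to the statement of 80% power for RNA-Seq and proteomic biomarkers. The protocol gives no alpha for that statement and does not tie it to Phase 3b attendance, so the extension is not supported.

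Two further replies stand in part. The planned mixed model can use partial data, so a two-sample calculation with proportionally reduced n is approximate. The other three Table 4 rows print 100% even at 100 per group, so only one row is sensitive.

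**Conclusion.** The point holds as an unreconciled use of 800, with a consequence for one power figure. If the table of phases is followed with four groups of 200, the 95% for FEV1 in paraseptal emphysema requires every invitee to be analysed.

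The size depends on a return rate that the protocol does not give. At two-sided 0.05 the loss is small at 90-95% return (93-94%) and material at 77% (88%) or 54% (75%). At the p<0.01 criterion there is less margin to start with: about 85% at full attendance, falling to 80-82%, 72% and 53%.

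These figures rest on the effect back-solved from Table 4 (about 0.36 SD), a two-group normal approximation, and loss proportional across groups. Table 4's row is not miscalculated: it reproduces at two-sided 0.05. What is missing is an allowance for non-return and agreement with the stated criterion.

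**What to change.** Reconcile Specific Aim 3, the Phase 3b column of the table of phases, and the Short-Term Follow-Up text in Section VII. Either of two changes would do.

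1. Define 800 (200 per group, reference group included) as the number who complete Phase 3b, with the Data Coordinating Center's list continuing until each group reaches 200 or the pool is exhausted. The number of visits stays within the 800 planned. The cost is a longer invitation list.
2. Keep 800 as the number invited, and restate the paraseptal FEV1 power at the expected number of completers and at the alpha the analysis will use, showing the assumed return rate. The cost is one recalculated row and a sentence.

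Under either change, state the alpha used for Table 4, and say whether the reference group and the exacerbation subjects added under the COVID-19 Adaptation fall inside the 800.

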290 Non-smoker controls enrolled during the Phase 3 study will be assessed for eligibility using the
291 inclusion and exclusion criteria listed previously (Section III) for the new non-smoker controls.

292

293 **Table of Visit Procedures**

294

Procedure *forms are different for new nonsmokers	Phase 3a Visit- Return Subjects and New Nonsmokers	Phase 3b- Short Term Follow Up or post-COVID Follow-up	Phase 3 Modified- Virtual	Phase 3 Modified- In-Person
Eligibility*	X	X	X	X
Informed Consent/HIPAA	X	X	X	X
Confirmation of Final Eligibility	X	X	X	X
Medical Record Release Authorization	X	X		X
Subject Personal Information	X	X	X	
Demographics Form	X	X		X
Safety Assessment	X	X		X
Medical History*	X	X	X	
Medication History	X	X		X
Pre- and post- bronchodilator spirometry with albuterol	X	X		X

Procedure *forms are different for new nonsmokers	Phase 3a Visit-Return Subjects and New Nonsmokers	Phase 3b-Short Term Follow Up or post-COVID Follow-up	Phase 3 Modified-Virtual	Phase 3 Modified-In-Person
DLco	X	X		X
Respiratory Disease Questionnaire*	X	X	X	
Modified Respiratory Disease Questionnaire				X
Six Minute Walk Test	X	X		X
CAPTURE Questionnaire	X		X	
SF- 36 Questionnaire	X	X	X	
St. George's Respiratory Questionnaire (SGRQ)	X	X	X	
COPD Assessment Test (CAT)	X	X	X	
HADS	X	X		X
Cognitive Screen Items	X			X
Socioeconomic Questionnaire*	X		X	
PROactive Physical Activity Questionnaire	X	X	X	
Duke Activity Status Index (DASI)	X	X	X	
eCigarette Questionnaire	X	X	X	
Cannabis Questionnaire	X		X	
Optimism Questionnaire	X		X	
Residential and Occupational History*	X		X	
PTOA	X		X	
Blood Sample Collection	X	X		X

Procedure *forms are different for new nonsmokers	Phase 3a Visit-Return Subjects and New Nonsmokers	Phase 3b-Short Term Follow Up or post-COVID Follow-up	Phase 3 Modified-Virtual	Phase 3 Modified-In-Person
Sit to Stand Test	X	X		X
Hand Grip Strength	X	X		X
Food Frequency Questionnaire	X			X
CT Scan	X	X		X
COVID Questionnaire			X	
Dried Blood Spot			X	

295 During the Phase 3 research study visit, the following procedures will be performed (for return
 296 subjects and new non-smokers):

297 1. Informed consent and HIPAA authorization will be obtained prior to any other study
 298 procedure. An updated authorization to obtain medical records to adjudicate the cause of
 299 death will be obtained. Subjects will be asked to provide a signed release of medical

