438 and plasma (for measurement of other proteins potentially related to COPD and other
439 diseases) and a CBC (complete blood count). A total volume of up to 50 ml of blood will
440 be drawn for this study. A complete blood count will be performed at the Clinical Centers.
441 The rest of the blood samples will be stored at the COPDGene Biological Repository at
442 Brigham and Women's Hospital. Blood count results will be sent to the subject. If results
443 from the blood counts are felt to be clinically significant, they will also be sent to the
444 subject's primary care provider. Subjects without clinically significant results will be
445 asked to consent if they would like their blood count results sent to their primary care
446 physician. We will ask the subject what time of day they last ate and/or drink anything
447 other than water; including candy/chewing gum, and collect this information.

448 A dried blood spot kit will be sent to the participants who have agreed to provide a blood
449 sample. The kit will include an alcohol swab, lancets, sample collection card, card sleeve,
450 band-aid, instructions, return envelope, and a copy of the informed consent.

451 Subsequent blood spot kits will be sent to participants who have had an inconclusive result
452 on their previous antibody test(s) or lost/damaged the kit. Blood spot kit(s) will be sent to
453 participants to survey for COVID antibodies at up to 12-month intervals when COVID
454 remains in an epidemic status and extend into antibody surveys at up to 12-month
455 intervals during the first five years of endemic circulation of COVID.

456 11. Six-Minute Walk Test will be performed in a standardized manner on all subjects to
457 determine exercise capacity (11). Subjects will be asked questions to assure they do not
458 have significant or occult heart disease prior to the test to assure subject safety. Subjects
459 who have significant cardiovascular disease may require evaluation by the local physician

460 investigator prior to six-minute walk test. Immediately after and one minute after the end
461 of the six-minute walk test, a subject's heart rate and oxygen saturation will be measured
462 using a pulse oximeter. Subjects who use > 6 L/min oxygen flow with activity will not
463 perform the Six- Minute Walk Test.

464 12. Chest CT Scans will be performed to assess emphysema and airway disease in all subjects.

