829 information to the Data Coordinating Center (DCC). Pulmonary function and questionnaire data,

830 identified by study ID number only, will be transferred by secure internet connection (with 132-
831 bit encryption) to the Data Coordinating Center at National Jewish Health in Denver. Identifying
832 information will be sent from the Clinical Centers to the DCC, but this identifying information
833 will be stored separately from clinical and genetic information collected in COPDGene. Study
834 personnel at Clinical Centers and the DCC will be required to meet local requirements for
835 training in protection of confidentiality.

836 Potential risks of blood drawing are hematoma at the skin site and minimal pain of venous
837 puncture.

838
839 Risks associated with the dried blood spot kit include slight discomfort when using the lancet
840 (people have described the feeling as a slight sting – much less than you would experience in a
841 typical blood draw) and, as with any cut, there is a small risk of infection and/or bruising.
842 However, the process and products in the kit are used routinely in a wide range of healthcare
843 applications, including measurement of blood glucose in diabetes. The equipment is sterile and
844 following the instructions provided in the kit (like cleaning the area) will minimize infection risk.

845 Radiation exposure in the chest CT scan could theoretically increase the risk of cancer. Exposure
846 of pregnant women to CT scan radiation could be harmful to the developing fetus. To minimize
847 the likelihood of exposing pregnant women to CT scans, females of child-bearing potential will
848 be asked if they are pregnant or have the possibility of being pregnant before the chest CT scan.
849 CT scans will not be performed for women who state they are pregnant or that they may be
850 pregnant; other pre-menopausal women will undergo urine pregnancy testing before a chest CT
851 scan is performed. Chest CT scans could identify pulmonary nodules that may require follow-up
852 outside of this study. Such pulmonary nodules could be curable lung cancers (a benefit) or
853 scars/prior granulomas that could require additional radiation exposure or even surgery (a risk).

854 The maximum amount of radiation exposure, during the chest CT scan is approximately 7 mSv
855 at each study visit. The radiation dose differs with body size; thinner subjects will have less than

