883 approval and with requirements to maintain subject confidentiality. Subject-identifying
884 information will not be transmitted to other investigators. A Certificate of Confidentiality has
885 been obtained for the COPDGene study to provide additional protection for study participants.

886 **IX. POTENTIAL BENEFITS**

887 There are no expected benefits to the study participants. Improved understanding of COPD has
888 occurred; COPDGene has generated over 230 scientific publications. As noted above, CT scans
889 could identify pulmonary nodules, early lung cancer or other abnormalities that may require
890 follow-up outside of this study.

891 **X. MONITORING AND QUALITY ASSURANCE**

892 This is an observational longitudinal investigation without a therapeutic intervention. It is
893 expected that there will be deaths in both control and COPD subjects enrolled in this study that
894 are not related to study procedures. It is expected that there will be hospitalizations from a
895 variety of causes not related to study procedures including but not limited to newly discovered
896 disorders, acute disorders requiring surgery, pre-existing conditions, and exacerbations of
897 underlying COPD. Subjects may expire due to pre-existing or new diseases including cancer,
898 cardiovascular conditions, and COPD. These are anticipated events that are not related to this
899 investigation. These events will not be prospectively collected as part of the current study and
900 thus will not be reported to IRBs. Adverse events for the purposes of this study will only be
901 those that are directly related to study procedures done during the study visit(s). There are no
902 expected Serious Adverse Events in this study related to study procedures. At each Clinical
903 Center, subjects will be observed for the development of tremulousness, and nervousness
904 following bronchodilator medication. Unexpected Adverse Events related to study procedures
905 will be reported to the IRB of the Clinical Center and to the Executive Committee. An
906 Observational Safety and Monitoring Board (OSMB) has been appointed by the National Heart,
907 Lung, and Blood Institute and will continue to oversee this study. All protocol deviations and
908 adverse events will be reviewed by the OSMB, and the OSMB will vote on modifying the study
909 if needed.

910 Quality assurance of spirometry data will be insured by the Pulmonary Function Core at National

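### Section X ties adverse events to study visits, so read literally it misses complications of dried blood spot kits used at home outside any visit

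*Protocol*

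**What the plan says.** Section X (Monitoring and Quality Assurance) first sets aside background deaths and hospitalizations. It then defines adverse events exclusively: they are only "those that are directly related to study procedures done during the study visit(s"). Two reporting routes follow. "Unexpected Adverse Events related to study procedures" go to the clinical center's IRB and to the Executive Committee. Protocol deviations and "adverse events will be reviewed by the OSMB, and the OSMB will vote on modifying the study" if needed. The section also says that there are no "expected Serious Adverse Events in this study related to study procedures".

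The dried blood spot kit is described in Section V, item 10, and in Section VI under COVID-19 Adaptation and Mail Consent. It is posted to the participant, who pricks a finger and sends the card back. Replacements follow an inconclusive result or a lost or damaged kit. Further kits go to "participants to survey for COVID antibodies at up to 12-month intervals when COVID" remains epidemic, and the surveys continue at such "intervals during the first five years of endemic circulation of COVID". Staff help is an option if the participant happens to be on site when a sample is due. Section VI also allows people with no Phase 3 visit scheduled to consent through a separate COVID-19 tracking contact.

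Section VIII discloses the kit's risks. It puts the lancet's discomfort well below that of a "typical blood draw) and, as with any cut, there is a small risk of infection and/or bruising".

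**The concern.** The definition applies two tests at once: the event must be related to a study procedure, and that procedure must have been done during a visit. A self-administered finger-prick at home can meet the first test and fail the second. Section VIII treats the kit as a procedure with risks of its own, yet nothing in Section X extends the definition to its use at home.

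What is at stake is the completeness of a small part of safety oversight. The OSMB reviews what the definition admits. If an infected or badly bruised finger after a mailed kit is not an adverse event under the protocol, no rule requires that the board see it.

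**Working it through.** No arithmetic applies, and the plan gives no figure to reproduce. The check sets the definition beside each use of the kit and then follows the reporting routes.

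**1. Is the definition exclusive?** Yes. Section X says that adverse events are only those meeting the stated condition, and the visit is part of that condition.

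**2. Which kit uses meet it?**

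- *Finger-prick done on site during a visit* (Section VI, COVID-19 Adaptation): inside the definition.
- *Kit tied to the virtual visit*: arguably inside. The Table of Visit Procedures in Section V marks Dried Blood Spot under the Phase 3 Modified-Virtual column, and only there.
- *Replacement kits* (Section V, item 10): triggered by a test result or a lost or damaged kit, not by a visit. Outside on a literal reading.
- *Repeat antibody-survey kits* (Section V, item 10; Section VI): triggered by the calendar. Outside on a literal reading unless the sample happens to be taken on site.
- *Kits for people reached only through the separate COVID-19 contact* (Section VI): the protocol describes these people as having no Phase 3 visit scheduled. Outside on a literal reading.

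**3. Does the list heading bring the last three back in?** Item 10 stands in a list that opens "During the Phase 3 research study visit, the following procedures will be performed (for return" subjects and new non-smokers). The same list holds activities plainly not done during a visit. Item 9 hands out the food frequency questionnaire after the visit, for completion at home if preferred. Item 17 is a COVID questionnaire prompted by a longitudinal follow-up call. Being in the list therefore does not show that something is done during a visit.

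**4. What happens to an event outside the definition?**

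- *OSMB*: its review covers adverse events, the defined term. An event outside the definition need not reach it.
- *IRB and Executive Committee*: that sentence does not repeat the visit limit, which favors coverage. It does use the term just defined, which counts against it. Coverage of an unexpected kit event is arguable but not certain. The disclosed harms, infection and bruising, are expected ones and would not travel by this route.
- *Longitudinal follow-up contacts* (Section VI): these ask about health status and new illnesses, so an infection might come to light. Learning of it does not make it an adverse event under Section X.

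**5. Is the visit limit needed?** No. The requirement that an event be directly related to study procedures already excludes background deaths and hospitalizations, which is the purpose of the surrounding sentences.

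**The case against.** The best defense is that the protocol itself treats the kit as a visit procedure. It has a row in the Table of Visit Procedures, its text stands in the visit list, and Section VIII sets its risks beside those of the other procedures. In context, the definition separates procedure-related events from background illness, and nothing suggests an intent to exclude a procedure because of where it is done. A narrow scope for adverse events is also defensible in an observational study with no therapeutic intervention.

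Part of this stands. The exclusion is probably unintended, and a kit tied to the virtual visit may well be covered. The argument from the list and table does not close the gap, because the list holds items done outside visits and the table marks the kit only under the virtual visit. A probable intention also does not change wording that is stated as exclusive.

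A reader might infer that serious or unexpected kit complications would go unreported. The documents do not support that. Section X expects no serious procedure-related events, so a serious one would be unexpected, and the sentence on unexpected events does not repeat the visit limit. A reader might also infer that every kit use is excluded, or that participants have nowhere to report a problem. On-site samples are covered, and the kit instructions and enclosed consent copy are not available to judge.

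**Conclusion.** The point holds as a minor gap in wording. Read literally, the definition leaves out complications of repeat survey kits, replacement kits, and kits for people reached only through the separate COVID-19 contact, when these are used at home outside any visit. Such events need not reach the OSMB, and their route to the IRB and Executive Committee if unexpected is open to argument.

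The consequence is small. The disclosed harms are slight, and no endpoint, estimate or eligibility rule depends on the definition. The documents give no complication rate, so no amount of harm can be stated. The conclusion assumes that the words of Section X are applied as written and that no other instruction to the sites, outside this protocol, widens them. It is a cheap improvement, not a fault that puts the study's results or its participants' safety in doubt.

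**What to change.** In Section X, define adverse events as those *directly related to study procedures, whether done during a study visit or at home with a mailed dried blood spot kit*. State that any such kit events that are reported are included in the OSMB review.

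This costs one phrase in the definition, a short addition on OSMB review, and the logging of a few minor events. It needs no new procedure or participant contact, and background deaths and hospitalizations stay excluded because they are not directly related to study procedures.
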